2.4. Pooling Algorithm for Analysis Centers

Subjects will be enrolled at sites in the United States (US). Actual site enrollment rates will be monitored to avoid gross imbalances across centers. Sites will not be pooled for analyses.

2.5. Analysis Sets

Subjects will be classified into the following analysis sets: all randomized, full analysis set, and safety analysis set.

2.5.1. All Randomized Analysis Set

The all randomized analysis set includes all subjects who were randomized in the study (i.e., subjects who reported a randomization date, or were assigned a randomization number) regardless of whether or not study agent was received.

2.5.2. Efficacy Analysis Set

2.5.2.1. Full Analysis Set

The full analysis set includes all randomized subjects who received at least 1 dose of study agent except subjects who received potentially defective investigational products (IP) and were subsequently discontinued early because of the IP issue.

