### Efficacy Analysis

The efficacy analyses will be based on the full analysis set (FAS) which consists of all subjects who were randomly assigned to study drug and received at least 1 dose of study drug.

The primary efficacy endpoint, time to all-cause discontinuation of study drug, will be estimated by the Kaplan-Meier method and summarized (number of discontinuations, number of censored subjects, median, 25th and 75th percentile, if estimable) by treatment group. Time to all-cause discontinuation of study drug is defined as the number of days from the first dose of study drug to the last dose of study drug. Subjects who complete treatment are not considered to have discontinued. A stratified log-rank test (stratified for baseline insomnia status) will be used to test the hypothesis that there is no difference between the JNJ-42847922 group and quetiapine XR in the probability of discontinuing study drug, using a 1-sided 0.10 significance level.

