### **11.1. Subject Information**

The efficacy analyses will be based on the full analysis set (FAS) which consists of all subjects who were randomly assigned to study drug and received at least 1 dose of study drug.

Safety analyses will be based on the safety analysis set, which consists of all subjects who were randomly assigned to study drug and received at least 1 dose of study drug. The safety analysis set is the same as the FAS.

For all subjects who are randomly assigned to study drug, descriptive statistics (eg, study completion/withdrawal information, demographic and baseline data) will be provided.

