### **11.3. Efficacy Analyses**

The primary efficacy endpoint, time to all-cause discontinuation of study drug, will be estimated by the Kaplan-Meier method and summarized (number of discontinuations, number of censored subjects, median, 25th and 75th percentile, if estimable) by treatment group. Time to all-cause discontinuation of study drug is defined as the number of days from the first dose of study drug to the last dose of study drug. Subjects who complete treatment are not considered to have discontinued. A stratified log-rank test (stratified for baseline insomnia status) will be used to test the hypothesis that there is no difference between the JNJ-42847922 group and quetiapine XR in the probability of discontinuing study drug, using a 1-sided 0.10 significance level.

The analyses for the secondary efficacy endpoints will be described in the SAP. For all other efficacy endpoints, no multiplicity adjustment will be done and nominal p-values will be presented.

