2.5.3. Safety Analysis Set

The safety analysis set includes all randomized subjects who received at least 1 dose of study agent.

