4. SUBJECT INFORMATION

The number of subjects in each analysis set will be summarized and listed by treatment group and overall. In addition, the distribution of subjects by site ID will be presented for the full analysis set.

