4.2. Disposition Information

The number of screen failures will be summarized overall.

The number of subjects in the following disposition categories will be summarized throughout the study by treatment group and overall:

- Subjects randomized
- Subjects receiving study agent
- Subjects who completed the double-blind phase
- Subjects who discontinued from the double-blind phase
 - Reasons for discontinuation from the double-blind phase
- Subjects completing the follow-up phase

Listings of subjects will be provided for the following categories:

- All randomized subjects
- Subjects who discontinued from the double-blind phase
- Subjects who discontinued from the follow-up phase
- Subjects who were unblinded during the study period
- Subjects who were randomized yet did not receive study agent.

These summaries and listings will be provided for the all randomized analysis set.

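### The SAP full analysis set drops treated subjects stopped over suspect product, so membership in the primary time-to-discontinuation analysis depends on the outcome

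*SAP*

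**What the plan says.** Protocol 11.1 bases efficacy on a FAS "which consists of all subjects who were randomly assigned to study drug and received at least 1 dose of study drug" and adds: "The safety analysis set is the same as the FAS". The Synopsis (Efficacy Analysis) defines the FAS in the same way.

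The SAP splits the two sets. Section 2.5.3 keeps the protocol rule for safety: "The safety analysis set includes all randomized subjects who received at least 1 dose of study agent". Section 2.5.2.1 takes the same subjects for the FAS "except subjects who received potentially defective investigational products (IP) and were subsequently discontinued early because of the IP issue". SAP 5 puts all efficacy analyses on that FAS, and 5.2.2 repeats this for the primary analysis. The estimand in 5.2.2 does not mention a product-related stop.

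SAP 5.2.3 counts every discontinuation of the double-blind phase as an event at the last dose, whatever the reason, and censors completers. Protocol 11.3 likewise exempts only completers: "Subjects who complete treatment are not considered to have discontinued".

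The excluded subjects remain visible elsewhere. SAP 4 states "The number of subjects in each analysis set will be summarized and listed by treatment group and overall", SAP 4.2 gives reasons for discontinuation on the all-randomised set, and SAP 4.4 covers exposure and lists dosing by subject.

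**The concern.** In most trials, removing subjects because of a supply fault costs some sample size. Here the endpoint is staying on drug, and a subject can be stopped over a product problem only if still on drug. Three subjects given the same suspect product are handled differently:

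- one who had already discontinued for another reason stays in as an event;
- one who had already completed stays in as censored;
- one still on treatment at the stop is deleted, with all follow-up.

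The deletion removes event-free time and no events, so it raises the apparent discontinuation rate in any affected arm. If the arms are affected unequally, the comparison shifts. It favours JNJ-42847922 when quetiapine XR is the affected arm and works against it in the reverse case. The exclusion does not even give a clean-product population, because exposed subjects with earlier events remain.

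Nothing in SAP 5.2.3 or 5.2.3.1 repairs this. The unstratified log-rank test, the optional site exclusion, the Cox models, the Week 12 curves, the analysis of treatment-related discontinuation and the subgroups all use the same FAS. The tables in SAP 4, 4.2 and 4.4 would reveal an imbalance but would not correct the test.

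**Working it through.** **The plan's own figure** (SAP 1.4: 50 per arm, 50% discontinuation on quetiapine XR, HR 0.415, 1-sided 0.10).
- JNJ-42847922 discontinuation = 1 − 0.5^0.415 = 25.0%. Expected events = 25 + 12.5 = 37.5.
- Power = Φ(√37.5/2 × |ln 0.415| − 1.282) = Φ(2.693 − 1.282) = 92.1%, against about 92% stated.
- The SAP's two-sided 0.20 level uses the same critical value.

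**Assumptions.** The documents give no count, arm or date, so everything below is assumed: exponential discontinuation with λ = ln 2/168 per day on quetiapine XR, administrative censoring at Day 168, and product stops uniform over Days 14–154 unless the subject has already discontinued.

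**How many are deleted.** On quetiapine XR, P(stop comes first) = (e^(−14λ) − e^(−154λ))/(140λ) = (0.944 − 0.530)/0.578 = 0.717. Of 2, 5, 10 or 20 affected subjects, 1.4, 3.6, 7.2 or 14.3 are deleted.

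**Effect on the crude rate** (quetiapine XR, true value 50%).
- 10 affected: (20 + 2.83)/(50 − 7.17) = 53.3%.
- 20 affected: (15 + 5.66)/(50 − 14.34) = 57.9%.

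**Effect on the test.** Log-rank simulation, 12,000 replicates per scenario. With no product problem, rejection is 9.4–10.5% at HR 1 and power is 91–92% at HR 0.415.

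| Affected | 2 | 5 | 10 | 20 |
|---|---|---|---|---|
| Quetiapine XR only, HR 1: excluded | 10.7% | 13.5% | 18.3% | 32.2% |
| same: mean estimated HR, excluded | 0.99 | 0.95 | 0.90 | 0.78 |
| same: restored, counted as events | 13.3% | 21.8% | 39.1% | 79.6% |
| JNJ-42847922 only, HR 1: excluded | 9.4% | 7.4% | 5.0% | 1.6% |
| JNJ-42847922 only, HR 0.415, power: excluded | 90.3% | 88.0% | 82.8% | 65.7% |
| same: censored | 91.3% | 90.7% | 90.1% | 89.0% |
| Both arms (number per arm), HR 1: excluded | – | 9.6% | 10.1% | 9.4% |
| Both arms, HR 0.415, power: excluded | – | 90.5% | 88.8% | 85.2% |
| same: censored | – | 90.7% | 89.4% | 86.9% |

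Censoring at the stop holds one-arm rejection at HR 1 to 9.6–10.2% (quetiapine XR only) and about 10% (JNJ-42847922 only).

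A separate simulation with stops uniform over the 24 weeks (8,000 replicates) agrees. With 10 and 20 quetiapine XR subjects affected, exclusion gives 17.4% and 31.3%. With 20 JNJ-42847922 subjects affected, power is 65.5% with exclusion and 88.8% with censoring.

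**Milder cases** (HR 1, exclusion).
- Quetiapine XR only, stops on Days 1–28: 11.2%, 11.6% and 14.9% for 5, 10 and 20 affected.
- Quetiapine XR only, stop days spread over 14–300, so that 62% of affected subjects never have a product stop: 13.8% and 19.6% for 10 and 20.
- Ten affected, split 6/4 or 7/3 towards quetiapine XR: about 11% and 13%.

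**If affected subjects have a different prognosis** (HR 1 otherwise).

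| Affected group | Hazard | Censored | Excluded |
|---|---|---|---|
| 10 quetiapine XR | ×0.5 | 6.3% | 14.3% |
| 10 quetiapine XR | ×2 | 17.5% | 24.9% |
| 20 quetiapine XR | ×0.5 | 3.5% | 21.1% |
| 20 quetiapine XR | ×2 | 28.2% | 51.5% |
| 10 JNJ-42847922 | ×0.5 | 14.1% | 7.2% |

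**Why the wider set should not simply be carried into the secondary analyses.** Assume 30% sustained response, which requires reaching Week 24, and 10 affected in one arm. The SAP FAS reads (40 × 0.3)/(50 − 7.17) = 28.0%. Restoring these subjects as non-responders, as SAP 5.1.2 would, reads 12/50 = 24.0%. With 20 affected the figures are 9/35.66 = 25.2% and 9/50 = 18.0%.

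**The case against.** The strongest reply is that materiality is unproven. Every large figure needs a one-arm problem, and the largest need 20 of 50 subjects in that arm. A two-arm fault is just as easy to read from the documents: all tablets are over-encapsulated, and the lower-dose regimens in both arms include a placebo capsule (Protocol 6 and 14.1). In that case the null error is preserved and exclusion costs at most 1.7 points of power against censoring. This stands as a limit on size. It does not rule out a fault confined to one active product.

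The rule also looks deliberate. Neither SAP amendment lists a change to 2.5.2.1, and follow-up on suspect product need not represent the assigned treatment. That would justify setting such follow-up aside evenly. It does not justify a rule that keeps exposed subjects with events and deletes exposed subjects without them.

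Censoring departs from the protocol's all-cause definition and assumes that stopped subjects share the others' hazard. This stands too. In the quetiapine XR checks censoring lies nearer 10% than exclusion, though only slightly with 10 affected and half the hazard (3.7 against 4.3 points away). When the affected subjects are on JNJ-42847922 with half the hazard, censoring is no better (14.1% against 7.2%).

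A lighter remedy would leave the primary analysis alone and add the censored version as a sensitivity analysis. It would expose a distortion but leave the headline test on an outcome-dependent population. The recommended fix also leaves two populations in use across the efficacy analyses, with some distortion remaining in the secondary ones.

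**Conclusion.** The concern holds. The SAP narrows the protocol FAS, does so by a condition tied to the primary endpoint, and plans no time-to-event analysis that restores the lost follow-up.

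The size cannot be computed from the documents. Under the stated assumptions it ranges from about nil (equal exposure in both arms, or about 2 subjects affected) to rejection of a true null at 32.2% or 1.6% against a nominal 10%, or power of 65.7% against about 92%, when 20 of 50 in one arm are affected. The direction follows the affected arm.

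This should be fixed, with medium confidence: the flaw is clear from the text, its consequence depends on facts not given, and the correction is cheap. It should be settled under blind, before anyone knows which arm it favours.

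**What to change.** For the primary time-to-discontinuation analysis only, and as a pair:

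- include every randomised subject with at least one dose, analysed by randomised treatment (not the actual-treatment rule that SAP 6 applies to the safety set);
- censor at the last dose before a product-mandated stop.

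Write this into SAP 5.2.2 and 5.2.3 as an intercurrent-event rule and an explicit exception to counting every discontinuation as an event, with a matching exception in SAP 5. State that it departs from the protocol's all-cause endpoint. Do not make the first change without the second: counting product stops as events distorts more than the present exclusion (39.1% against 18.3% with 10 quetiapine XR subjects affected).

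Flag affected subjects under blind, and keep the current exclusion as a sensitivity analysis. Leave 2.5.2.1 in force for the other efficacy analyses, unless the non-responder (5.1.2), baseline-carried-forward (5.3.1.2) and sustained-response (5.3.3.2) rules are also revised to say how product stops are handled.

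The cost is SAP text, one blinded flag and one extra run, with no new data. The trade-offs are some follow-up on suspect product in the primary analysis, the similar-prognosis assumption, and about 3 points of power (92% to 89%) if 20 of 50 JNJ-42847922 subjects were affected.

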2.5.3. Safety Analysis Set

The safety analysis set includes all randomized subjects who received at least 1 dose of study agent.

2.6. Definition of Subgroups

Subgroup	Definition
Baseline ISI score	
 • ≥ 15 • < 15 using the randomization stratification factor as entered into IWRS; this will also be used in the analyses as the baseline insomnia status
Baseline MADRS total score	
 • \leq median • $>$ median
MDD subtype based on SCID-CT	
 • With anxious distress • Without anxious distress based on the Structured Clinical Interview for Diagnostic and Statistical Manual of Mental Disorders-Fifth Edition (DSM-5) Axis I Disorders – Clinical Trials Version (SCID-CT)
Sex	
 • Male

Subgroup	Definition
	
 Female Undifferentiated
Age Group	
 18-34 35-54 55-64 65-70
Sex and Age Group	
 Adults (18-64) male, Elderly (≥ 65) male, Adults (18-64) female, Elderly (≥ 65) female
MDD with Anxiety based on HAMA-A	
 Yes, defined as baseline HAM-A total score ≥ 18 No, defined as baseline HAM-A total score < 18
Class of antidepressant study medication	
 SNRI SSRI
Final dose	
 Seltorexant 20mg Seltorexant 40mg Quetiapine XR 150mg Quetiapine XR 300mg
Number of antidepressants of sufficient dose and with inadequate response taken for at least 4 weeks during the current episode	
 1 2 or more based on the Massachusetts General Hospital-Antidepressant Treatment Response Questionnaire (MGH-ATRQ)
Number of major depressive episodes in lifetime, including current episode	
 ≤ 3 > 3
Prior medication use of adjunctive antipsychotics	
 Yes No
Prior medication use of benzodiazepines	
 Yes No
Baseline body mass index (BMI)	
 underweight $< 18.5 \text{ kg/m}^2$ normal $18.5 - < 25 \text{ kg/m}^2$ overweight $25 - < 30 \text{ kg/m}^2$ obese $\geq 30 \text{ kg/m}^2$
Race	
 categories as collected on eCRF
Ethnicity	
 categories as collected on eCRF

2.7. Study Day and Relative Day

Study Day 1 or Day 1 refers to the start of the first study agent administration. All efficacy and safety assessments at all visits will be assigned a day relative to this date.

Study day or relative day for a visit is defined as:

- Visit date - (date of Study Day 1) +1, if visit date is \geq date of Day 1
- Visit date - Date of Day 1, if visit date $<$ date of Day 1

There is no 'Day 0'.

2.8. Baseline and End point (DB)

Baseline is defined as the last observation prior to the start of the first study agent administration, with the exception of the average predose ECG measurement and the average predose CSD-M measurement, which is defined as the average of all predose ECG results collected up to and

including the day of the first dose of study agent and the average of all predose CSD-M measurements collected up to and including the day of the first dose of study agent, respectively.

End point (DB) is defined as the last available postbaseline result within the double-blind phase. Unscheduled visit results are included in this definition and will be considered as the end point value if the unscheduled visit result is the last postbaseline result available within the double-blind phase.

2.9. Imputation Rules for Missing AE Date/Time of Onset/Resolution

Partial AE onset dates will be imputed as follows:

- If the onset date of an AE is missing day only, it will be set to:
 - First day of the month that the AE occurred, if month/year of the onset of AE is different than the month/year of the study agent start
 - The day of study agent start, if the month/year of the onset of AE is the same as month/year of the study agent start date and month/year of the AE resolution date is later
 - The day of study agent start or day of AE resolution date, whichever is earliest, if month/year of the onset of AE and month/year of the study agent start date and month/year of the AE resolution date are same.
- If the onset date of an AE is missing both day and month, it will be set to the earliest of:
 - January 1 of the year of onset, as long as this date is on or after the study agent start date
 - Month and day of the study agent start date, if this date is the same year that the AE occurred
 - Last day of the year if the year of the AE onset is prior to the year of the study agent start date
 - The AE resolution date.
- Completely missing onset dates will not be imputed.

Partial AE resolution dates not marked as ongoing will be imputed as follows:

- If the resolution date of an AE is missing day only, it will be set to the earliest of the last day of the month of occurrence of resolution or the day of the date of death, if death occurred in that month.
- If the resolution date of an AE is missing both day and month, it will be set to the earliest of December 31 of the year or the day and month of the date of death, if death occurred in that year.
- Completely missing resolution dates will not be imputed.

AE onset/resolution dates with missing times will be imputed as follows:

- A missing time of onset of an AE will be set to:

- 00:01 as long as the onset date is different from the study agent start date
- The time of the study agent start if this is the same day the AE occurred.
- The missing time of resolution of an adverse event will be set to 23:59.

If a missing time is associated with a partial or missing date, the date will be imputed first prior to imputing the time.

2.10. Imputation Rules for Missing Prior/Concomitant Medication Dates

2.10.1. Prior Medications

Prior medications or therapy are those taken by subjects before the start of dosing of first study agent. Medications will be classified as prior if the medication start date is complete and prior to the date of first dose of study agent or the medication end date is complete and prior to the date of first dose of study agent.

If the medication start day is missing, and the month and year of the start date are not missing, then if:

- The month and year of the start date of medication is earlier than the month and year of the initial study agent administration; or
- The CRF indicates the medication was taken prior (prior medication flag=Yes) and the month and year of the start date of medication is the same as the month and year of the initial study agent administration

then the medication will be considered prior.

If the medication start month and day are missing, and the year of the start date is not missing, then if:

- The year of the start date of medication is earlier than the year of the initial study agent administration; or
- The CRF indicates the medication was taken prior when the year of the start date of medication is the same as the year of the initial study agent administration

then it will also be considered prior.

If the medication start date is completely missing, and the CRF indicates it was taken prior, it will also be considered prior.

2.10.2. Concomitant Medications Taken During the Double-blind Phase

Concomitant medications taken during the double-blind phase are those that started on the same day as the first dose or after the start of dosing or those continuing from predose (prior medication flag=Yes) and the CRF indicates the medication is ongoing or the medication stop

date is on or after the first dose of study agent. Medications that start after the analysis reference end date of the double-blind phase are not considered concomitant medications taken during the double-blind phase.

If the medication start date is missing the day, but the month and year are complete, then if the month and year of the start date are on or prior to the month and year of the analysis reference end date of the double-blind phase and:

- The CRF indicates that the medication is ongoing, or
- The stop date of the medication is missing, or
- The stop date of the medication is on or after the initial study agent administration, or
- The stop date month and year (day is missing) of the medication is on or after the initial study agent administration, or
- The stop date year (day and month are missing) of the medication is on or after the initial study agent administration

then the medication is classified as concomitant during the double-blind phase.

If the medication start date is missing the month and day, but the year is complete, then if the year of the start date is the same as or prior to the year of the analysis reference end date of the double-blind phase and:

- The CRF indicates that the medication is ongoing, or
- The stop date of the medication is missing, or
- The stop date of the medication is on or after the initial study agent administration, or
- The stop date month and year (day is missing) of the medication is on or after the initial study agent administration, or
- The stop date year (day and month are missing) of the medication is on or after the initial study agent administration

then the medication is classified as concomitant during the double-blind phase.

If the medication start date is completely missing then if:

- The CRF indicates that the medication is ongoing, or
- The stop date of the medication is missing, or
- The stop date of the medication is on or after the initial study agent administration, or

- The stop date month and year (day is missing) of the medication is on or after the initial study agent administration, or
- The stop date year (day and month are missing) of the medication is on or after the initial study agent administration

then the medication is classified as concomitant during the double-blind phase.

For concomitant medications categorized as “taken during DB” based on the rules above, the duration during the DB phase will be calculated as: Minimum of medication end date and the DB End date - Maximum of the medication start date and the DB start date + 1. If there are partial start/end dates, the imputation rules for the duration during the DB phase are as follows:

If the month of the start date is not missing but the day is, then the duration is imputed as:

Minimum of the medication end date and the DB End Date - Maximum of the first day of the month and the DB Start Date + 1;

If the year of the start date is not missing but the month is, then the duration is imputed as:

Minimum of the medication end date and the DB End Date - Maximum of the first day of the year and the DB Start Date + 1;

If the month of the end date is not missing but the day is, then the duration is imputed as:

Minimum of the last day of the month and the DB End Date - Maximum of the medication start date and the DB Start date + 1;

If the year of the end date is not missing but the month is, then the duration is imputed as:

Minimum of the last day of the year and the DB End Date - Maximum of the medication start date and the DB Start date + 1.

